4. ESTIMATED DURATION OF THE STUDY

We estimate that the proposed study will take 5 years to complete. This includes completing data collection on 60 chronic low back pain patients, data analyses, and time for publication. Each participant will complete 7 study sessions, which includes review of medical records for confirmation of chronic low back pain, confirmation of study eligibility (i.e., positive response to the straight leg raise test, exclusion/inclusion criteria), baseline pain testing, four days of mental training (mindfulness/non-mindfulness) and two clinical visits where participants will be administered the straight leg raise test during placebo-saline or naloxone infusion. After all of the data has been collected, the investigators of the study will be unblinded and statistical analyses will be performed to test the study hypotheses at which point we will prepare the manuscript for publication.

We do expect recruitment to go smoothly and anticipate that data collection will be completed after 16 months which would provide ample time for data analyses and manuscript preparation.

With respect to the subject focused study procedures, a 4-subject cohort strategy would produce a start to finish accrual process of 1-2 months or less. An extra 2-3 weeks will be added to the schedule after one cohort completes to allow for the required accrual of the next group of 8 subjects. The total outside accrual boundary of this study, taking into account increased stringency with recruitment towards the end of the study and accounting for a 20% retention loss, is at an estimate of 12 months.

5. LAY LANGUAGE SUMMARY OR SYNOPSIS (no more than one paragraph)

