Drug Administration: All studies will be conducted with the supervision of ACTRI nurses in the ACTRI. As previously conducted (Zeidan, Adler-Neal et al. 2016), a 0.15mg/kg bolus dose of naloxone (Naloxone HCl, Amphastar Pharmaceuticals) or 25ml of normal saline will be administered over 10 minutes via the IV line of the antecubital vein of the non-dominant arm. Onset of naloxone-induced opioidergic antagonism occurs within 2 min of infusion and exhibits an average half-life of 64 min (Ngai, Berkowitz et al. 1976). To further ensure that naloxone will antagonize opioid receptors for the study entirety, we will administer a supplementary maintenance intravenous infusion dose of 0.15 mg/kg/h naloxone or saline immediately after bolus infusion ceases. The duration of the study from the onset of IV infusion to completion will be no more than 25 (average time of infusion = approx. 15 minutes). Only the study physicians, research pharmacist, and study coordinator will be aware of participant drug assignment.

Sample Size Determination & Power:

Assuming a conservative 20% dropout rate, we will recruit and randomize a total of 74 cLBP patients (n=37/group) to a mindfulness meditation or non-mindfulness meditation regimen. To conduct group comparisons among the two primary outcomes (naloxone + saline induced changes in pain intensity + unpleasantness) and to ensure an overall type I error rate < 0.05, we used conservative Bonferroni corrections (p= .025) in all power calculations. Employing the pilot data corresponding to preliminary findings and our previous work [22], we fit repeated measures ANOVA models that include indicator variables for group (mindfulness vs. non-mindfulness), drug (naloxone vs. saline), and session order. The estimated square root of mean square errors is 0.23 and 0.30 for pain intensity and pain unpleasantness, respectively. Thirty participants per group will provide 80% power to detect a group difference of 0.19 for pain intensity and 0.24 for pain unpleasantness. Such effect sizes are consistent with those observed from our pilot data. Statistical power will be also greater when pre-regimen pain ratings are entered as covariates to reduce residual variance.

Data Analyses and Interpretation:

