Primary Outcome: Age and sex will be entered as covariates in all appropriate analyses if between group differences exist. To test study hypotheses, a 2 (group) X 2 (rest vs. manipulation) X 3 (naloxone vs. saline) repeated measures (RM) ANOVA will be employed. Post-hoc paired samples t-tests (in each group) will be conducted to test the hypotheses that non-mindfulness meditation but not mindfulness induced analgesia will be reversed by administration of naloxone but not saline.

Exploratory analyses may be conducted (in supplementary papers) on the psychological assessments (Questionnaires for Study Assessments) to better appreciate the relationship in dispositional pain and the potential changes in pain responses due to the respective interventions.

Inclusion of Women and Minorities: Participants will include all sexes and races. We plan to screen from over 2500 cLBP patients from the ACTRI's pain recruitment service, 11 separate providers, and the local community. Based on the latest San Diego-based demographic consensus, we plan to recruit 60% White, 16% Asian, 7% Black, 0.5% Native American, 0.5% Pacific Islander, 12% Other race, 5% two or more races (We expect that 29% of our participants will be Hispanic or Latino). If necessary to obtain minority representation, under-represented racial groups will be targeted specifically for recruitment.

General Considerations:

Data for all individual participants randomized or exposed to study drug will be presented in data listings. Continuous data will be summarized using the following descriptive summary statistics: the number of subjects (n), mean, SD, SE, median, minimum value (min), and maximum value (max). Categorical data will be summarized using counts and percentages.

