15. RISK MANAGEMENT PROCEDURES AND ADEQUACY OF RESOURCES

The study was carefully designed to minimize or negate any potential risk/discomfort to participants.

An Independent Monitoring Committee (IMC) will monitor the activities of this study for purposes of evaluating subject safety and study integrity. The key elements of the IMC plan include protection of participant privacy, database protection, adverse event reporting, data quality and safety reports, participant compliance, and safety review plans. For the proposed study, the IMC will review the progress of and safety after 20, 40, 60 and 74 (if needed) study participants have completed all study procedures. There will be no fee for the independent monitoring of the proposed studies. [name] will oversee all experimental procedures of the proposed research activities. In the event of an adverse safety event, protocol deviations and adverse events will be promptly (less than 24 hours) reported to the IMC and the IRB.

This study will be stopped prior to its completion if: (1) the intervention is associated with adverse effects that call into question the safety of the intervention; (2) difficulty in study recruitment or retention will significantly impact the ability to evaluate the study endpoints; (3) any new information becomes available during the trial that necessitates stopping the trial; or (4) other situations occur that might warrant stopping the trial.

We do not anticipate any events that would cause a cessation of the study. We have repeatedly demonstrated the ability to reliably recruit, retain, and execute data collection in a fashion that ensures successful completion of our experiments.

However, in the unforeseeable case that the proposed study has to be stopped, the PI will include an assessment of futility in the annual progress report to NIH. We will consult with the IMC and NCCIH to assess the impact of significant data loss due to problems associated with stopping the study.

Straight Leg-Raise Test: The straight leg-raise test is a commonly employed maneuver to examine chronic low-back pain severity and patient mobility. In the rare case that pain exacerbation is increased by greater than 4 VAS points and does not return to baseline levels after 40 minutes, we will discontinue patient study participation with reimbursement and a physician will evaluate the participant.

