#### Exploratory outcome

- SF-12 Health Survey (SF-12): This is a 12-item version of the SF-36 item Health Survey designed to assess general mental and physical functioning, and overall health-related quality of life.

**Statistical Analysis Plan:** To test the primary hypotheses, a 2 (group) X 2 (rest vs. manipulation) X 3 (baseline vs. naloxone vs. saline) mixed model ANOVA will be employed to test differences in the change in pain from supine to straight leg raise test (SLR 1; SLR 2) within and across each testing session. Significant interactions will be explored using post-hoc paired simple effects tests to test the hypotheses that non-mindfulness meditation but not mindfulness induced analgesia will be reversed by administration of naloxone but not saline. Between group comparisons will also be explored with simple effects tests.

Secondary and exploratory outcomes will be assessed with a 2 (group) X 2 (baseline vs. post-intervention) by testing between and within group differences comparing baseline vs. post-study assessments. Simple effects tests will interpret significant main effects and interactions.

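### The protocol's RM ANOVA with paired t-tests, as usually fitted, drops participants missing a drug session, and the SAP's mixed model wording does not settle whether they are kept

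*Protocol*

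**What the plan says.** Protocol, section 9, Data Analyses and Interpretation: "a 2 (group) X 2 (rest vs. manipulation) X 3 (naloxone vs. saline) repeated measures (RM) ANOVA will be employed". The third factor has three levels but only two are named. For follow-up, "Post-hoc paired samples t-tests (in each group) will be conducted".

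SAP, Statistical Analysis Plan paragraph: "a 2 (group) X 2 (rest vs. manipulation) X 3 (baseline vs. naloxone vs. saline) mixed model ANOVA will be employed". This supplies the missing level, baseline. For follow-up, "Significant interactions will be explored using post-hoc paired simple effects tests".

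Expected loss appears twice. Section 9, Sample Size Determination & Power: "Assuming a conservative 20% dropout rate, we will recruit and randomize a total of 74 cLBP patients (n=37/group"). Section 4 gives an accrual estimate "accounting for a 20% retention loss". Section 10 gives the aim of keeping 60 of the 74. Randomisation follows Session 1 (section 9, Patient Randomization), so every randomised participant already has baseline ratings.

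Section 15 describes a rare case in which pain after the straight leg raise rises by more than 4 VAS points and has not returned to baseline after 40 minutes. In that case "we will discontinue patient study participation with reimbursement and a physician will evaluate the participant".

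Neither document gives an analysis set, an estimation method, a covariance structure or a missing-data rule. The only promise that covers all randomised participants concerns data listings (section 9, General Considerations).

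**The concern.** A classical repeated measures ANOVA needs every cell of a participant's record. A paired t-test of naloxone against saline needs Sessions 6 and 7. With either method, a participant who completes Session 6 and then leaves contributes nothing, although a valid rating under one drug was recorded.

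This matters more if leaving is related to pain. The leg raise is both the source of the primary outcome and the trigger of the section 15 stopping rule. A participant stopped at Session 6 could leave high ratings there and none at Session 7. Dropping such people removes the upper end of the pain distribution. The trial's own hypothesis, reversal of analgesia by naloxone in the non-mindfulness group only, means that high ratings, and so such losses, could be more frequent in one group. The completers would then no longer be the groups formed by randomisation.

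A likelihood-based mixed model keeps the Session 6 ratings and is valid under the weaker assumption that missingness depends only on observed data.

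**Working it through.** **Size of the loss.** 74 - 60 = 14, or 14/74 = 18.9%. From the stated rate, 60/(1 - 0.20) = 75, against 74 stated, and 74 x 0.80 = 59.2 completers. The plan's figure is reproduced to within rounding.

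**Power at the planned completer number.** Inputs from section 9: 30 per group, root mean square errors 0.23 and 0.30, differences 0.19 and 0.24, alpha 0.025 (taken as two-sided). The standardised distance is d / (SD x sqrt(2/30)).

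| Outcome | Normal | Noncentral t |
|---|---|---|
| Intensity, 0.19 / 0.23 | 0.831 | 0.813 |
| Unpleasantness, 0.24 / 0.30 | 0.804 | 0.785 |

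So 60 completers give about the stated 80% for the group comparison.

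**Gain for the group contrast (averaged over drug).** Assume 30 complete participants and k with one drug session per group, and a within-person correlation ICC of 0.3 to 0.7. In units of the rating variance, a participant with both sessions has a mean with variance v = (1 + ICC)/2, and a participant with one session has variance 1. With inverse-variance weights, the SE ratio is sqrt(30 / (30 + k v)).

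| k per group | ICC 0.3 (v = 0.65) | ICC 0.7 (v = 0.85) |
|---|---|---|
| 3 | sqrt(30/31.95) = 0.97 | sqrt(30/32.55) = 0.96 |
| 7 | sqrt(30/34.55) = 0.93 | sqrt(30/35.95) = 0.91 |

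**Gain for the naloxone-saline contrast and its interaction with group.** Assume 37 per arm, all with Session 1, 30 complete, q with one drug session (split evenly over the drugs), compound symmetry with correlation rho and no period effect. The contrast then has effective n = 30 + q / (2(1 + rho)).

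| q per arm | rho 0.3 | rho 0.7 |
|---|---|---|
| 0 | 30.0 | 30.0 |
| 2 | 30.8 | 30.6 |
| 4 | 31.5 | 31.2 |
| 7 | 32.7 | 32.1 |

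For an interaction of 0.22, taking 0.30 as the SD of the paired difference and alpha 0.025, power is 0.704 at n = 30, 0.747 at 32.7 and 0.804 at 37. The last value is not reached by any of these patterns.

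**Direction of bias, as an illustration only.** A large-sample simulation used SD 0.30, ICC 0.3 to 0.7, a naloxone effect of 0.22 in the non-mindfulness group and 0 in the mindfulness group, a true average group difference of 0.21, and Session 7 missing for those with the highest Session 6 ratings.

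| Session 7 missing | Completer group difference (true 0.21) |
|---|---|
| highest 5% | 0.18 to 0.19 |
| highest 10% | 0.16 to 0.17 |

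At 10%, the completer interaction was 0.20 to 0.21 (true 0.22). The likelihood estimate recovered about 0.21 and 0.22. Missingness here depends only on an observed rating, so the setting suits the likelihood model by construction.

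**The case against.** The SAP is the analysis document, and its phrase "mixed model ANOVA will be employed" may already mean a likelihood mixed model. Neither document says that incomplete participants are excluded. This stands: a reader might infer that the trial has committed itself to a completer analysis, but that rests on how the protocol's methods usually behave, not on a stated rule.

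The gain for the main hypothesis is small. Four training visits come before the first drug session, and anyone lost during them adds nothing to the naloxone-saline contrast under any model. The case of 7 partial participants per arm requires every loss to fall between Sessions 6 and 7. This also stands. A reader might infer that a mixed model restores the information of 74 people. It does not.

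The loss is a planning ceiling. The 20% is called conservative, past attrition is called low, and the enrolment target allows for it. So the inference that dropout leaves the group comparison short of power fails.

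On bias, the only documentary link between pain and leaving is the section 15 rule, which is described as rare and could also operate in Session 1, before randomisation. Nothing in the documents shows that loss will differ by arm. The simulation therefore shows direction, not a forecast.

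What remains is that the protocol names a method that is poorer under incomplete data, the SAP names one that can be read two ways, and loss after randomisation is expected.

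**Conclusion.** The point holds as a low-cost improvement and a reconciliation of two texts, not as proof that the planned result will be biased. The protocol's methods, as normally fitted, drop participants without both drug sessions, and the SAP leaves open whether they are kept.

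The main benefit of a defined likelihood model is less exposure to selection bias. The gain in precision is modest: about 3-9% off the standard error of the group contrast, and 0-9% in effective n for the naloxone-saline contrast. These ranges assume 3 to 7 (group contrast) or 0 to 7 (drug contrast) partial participants per group and within-person correlations of 0.3 to 0.7. The documents give neither the timing of loss nor the correlation. The frequency of pain-related stopping, and so the actual size of any bias, cannot be derived from them.

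**What to change.** Reconcile the protocol's Primary Outcome paragraph with the SAP's Statistical Analysis Plan paragraph by stating one model in both:

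- A linear mixed model fitted by REML on all randomised participants.
- Outcome: the change from supine to straight leg raise. Alternatively, use the raw ratings, keep the rest-versus-manipulation factor and add a random effect for session within participant.
- Session 1 kept as the baseline level of the three-level session factor, so that every randomised participant contributes to the model.
- Fixed effects: group, session/drug, their interaction, session order and sex. Session order is in the power model of section 9 (Sample Size Determination & Power) but in neither analysis plan. Sex is the randomisation stratum.
- A participant random effect, with the covariance structure stated.
- Simple effects taken as contrasts from this model in place of separate paired tests.
- The missing-at-random assumption stated, with one sensitivity analysis that departs from it.

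The cost is revised wording, somewhat more analysis work and reliance on an assumption that cannot be fully tested. No new data or visits are needed.

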Patients will return to the ACTRI to complete session 7 and will follow the same procedures (except for drug administration) as Session 6. Participants must wait 2 days to participate but no longer than 7 days to complete Session 7. Drug symptomology will be assessed after each session.

Primary Outcome Measure(s):

1. Visual Analog Scale (VAS) and numerical rating scales (NRS): Pain ratings (VAS pain intensity, VAS unpleasantness, and numerical pain ratings) will be assessed in response to the straight leg raise test.
2. exploratory outcomes include those corresponding to "heat induced pain ratings" (i.e. thermal stimulation), and lying supine. The minimum rating ("0") is designated as "no pain" whereas the maximum ("10") is labeled as "most intense imaginable" or "most unpleasant imaginable." Higher numbers correspond to higher pain.
 - a. We will collect naloxone and saline induced changes in pain intensity and pain unpleasantness ratings

Sample Size Determination: Our targeted sample size is 60 cLBP patients (30/group). To conduct group comparisons among the two primary outcomes (naloxone + saline induced changes in pain intensity + unpleasantness) and to ensure an overall type I error rate < 0.05, we used conservative Bonferroni corrections ($p = .025$) in all power calculations. Employing the pilot data corresponding to our previous work (Wells et al., 2020), we fit repeated measures ANOVA models that include indicator

variables for group (mindfulness vs. sham) and drug (naloxone vs. saline). The estimated square root of mean square errors is 0.23 (23%) and 0.30 (30%) for pain intensity and pain unpleasantness, respectively. Thirty subjects will provide 80% power to detect a pain rating difference of 22% between the naloxone and saline conditions in the non-mindfulness group with an estimated SD of 0.3 (30%). We expect no meaningful differences in pain reductions between naloxone and saline infusion during mindfulness meditation. Thus, we will have 80% power to detect a significant group X drug type interaction. Finally, 30 subjects/group will provide 80% power to detect a significant group difference of 19% for pain intensity and 24% for pain unpleasantness. Such effect sizes parallel those observed in our pilot data (Wells et al., 2020). Statistical power will be also greater when pre-regimen pain ratings are entered as covariates to reduce residual variance.

Questionnaires for Study Assessments:

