**Title:** Chronic Low Back Pain and Meditation

**NCT Record #:** NCT04034004

**Date:** May 3, 2023

**PI:** [name]

**Sample Size Determination:** Our targeted sample size is 60 cLBP patients (30/group). To conduct group comparisons among the two primary outcomes (naloxone + saline induced changes in pain ratings) and to ensure an overall type I error rate  $< 0.05$ , we used conservative Bonferroni corrections in all power calculations. Employing the pilot data corresponding to our previous work (Wells et al., 2020), we fit repeated measures ANOVA models that include indicator variables for group (mindfulness vs. non-mindfulness) and session (baseline vs. naloxone vs. saline). The estimated square root of mean square errors is 0.23 (23%) for pain ratings. Thirty subjects will provide 80% power to detect a pain rating difference of 22% between the naloxone and saline conditions in the non-mindfulness group with an estimated SD of 0.3 (30%). We expect no meaningful differences in pain reductions between naloxone and saline infusion during mindfulness meditation. Thus, we will have 80% power to detect a significant group X drug type interaction. Finally, 30 subjects/group will provide 80% power to detect a significant group difference of 19% for pain intensity. Such effect sizes parallel those observed in our pilot data (Wells et al., 2020).

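### No naloxone reversal under mindfulness is part of the primary hypothesis, but the only naloxone–saline test in that group is a paired test of difference, with no confidence-interval rule

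*Protocol*

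**What the plan says.** The Protocol (section 9, Data Analyses and Interpretation, Primary Outcome) tests the study hypotheses with a repeated measures ANOVA, and then: "Post-hoc paired samples t-tests (in each group) will be conducted to test the hypotheses that non-mindfulness meditation but not mindfulness induced analgesia will be reversed". No significant interaction is required first.

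The SAP (Statistical Analysis Plan paragraph) calls these the primary hypotheses. It uses a mixed-model ANOVA to "test differences in the change in pain from supine to straight leg raise test (SLR 1; SLR 2) within and across each testing session", with baseline, naloxone and saline as the levels of the session factor. It adds: "Significant interactions will be explored using post-hoc paired simple effects tests to test the hypotheses that non-mindfulness meditation but not mindfulness induced analgesia". Several interactions are possible in that model, and the SAP does not say which one opens the follow-up. It also plans between-group simple effects.

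On the mindfulness group, the SAP's sample size paragraph says "We expect no meaningful differences in pain reductions between naloxone and saline infusion during mindfulness meditation" and continues "Thus, we will have 80% power to detect a significant group X drug type interaction"; the Protocol's Sample Size Determination says the same. No number is attached to what counts as meaningful. The power statement for the drug comparison covers the other group only: "Thirty subjects will provide 80% power to detect a pain rating difference of 22% between the naloxone and saline conditions in the non-mindfulness group". The descriptive summaries listed in the Protocol include the SE but no confidence interval.

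**The concern.** The primary objective (Protocol section 6) asks whether mindfulness relief is opioid-mediated. The expected answer is no, and that negative is written into the tested hypothesis. None of the planned naloxone–saline tests can establish it:

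- The group-by-drug interaction shows that reversal differs between groups. A smaller reversal under mindfulness also produces it.
- The overall drug effect pools both groups.
- The paired test isolates the mindfulness group, but failing to find a difference in about 30 patients is not evidence of no difference.

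Section 7 of the Protocol treats an opioid role in patients as possible. Section 18 argues, conditionally, for combining mindfulness with conventional therapies if relief proves not to be opioid-mediated. Without a rule on what the data must exclude, a result compatible with partial reversal could be reported as that negative answer. Under the SAP's gate, there might be no mindfulness-specific result at all.

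**Working it through.** **The plan's own figure.** Difference 0.22, SD 0.30, 30 per condition treated as independent: SE = 0.30 × √(2/30) = 0.0775, and 0.22/0.0775 = 2.84. With 58 df this gives 79.8% power at two-sided .05 and 70.4% at two-sided .025. The stated 80% therefore reproduces at two-sided .05 (equivalently, one-sided .025). The Protocol says "we used conservative Bonferroni corrections (p= .025) in all power calculations" without giving sidedness.

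**The missing input.** The documents do not say whether 0.30 is a per-condition SD or the SD of paired differences. For a per-condition SD, SD of differences = 0.30 × √(2(1 − ρ)), where ρ is the within-patient correlation. Four values are carried through as assumptions:

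- 0.232: per-condition 0.30 with ρ = 0.7
- 0.300: 0.30 read as the SD of differences, or per-condition with ρ = 0.5
- 0.325: 0.23 × √2, taking "The estimated square root of mean square errors is 0.23 (23%) for pain ratings" as within-patient error
- 0.424: per-condition 0.30 with ρ = 0

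**Formulas.** Points are percentage points on the power-calculation scale, and tests are two-sided.

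- Paired test, n = 30: SE = SD/√30; noncentral t with 29 df and noncentrality (true reversal)/SE. Critical values are 2.045 (.05) and 2.364 (.025).
- Interval half-width: critical value × SE.
- Two-level group-by-drug contrast: SE = SD × √(2/30), 58 df.

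Example at SD 0.300: SE = 0.0548 and 0.11/0.0548 = 2.01 against 2.045, so an 11-point reversal is missed in 50.7% of trials. The 95% half-width is 2.045 × 0.0548 = 0.112.

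| SD of differences | 0.232 | 0.300 | 0.325 | 0.424 |
|---|---|---|---|---|
| 11-point reversal missed, .05 | 29% | 51% | 57% | 72% |
| 11-point reversal missed, .025 | about 40% | 62% | 68% | 81% |
| 22-point reversal missed, .05 | under 1% | 3% | 5% | 22% |
| 95% half-width, points | 9 | 11 | 12 | 16 |
| Interaction not significant, true 22 and 0, .05 | 5% | 20% | 27% | 49% |

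The 11 points is an assumption: half of the planned 22.

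**Interaction and paired test read together.** Suppose the true reversals are 22 (non-mindfulness) and 11 (mindfulness), with SD 0.30 to 0.424. By simulation at .05, the interaction is significant in 17 to 29% of trials. A significant interaction together with a non-significant mindfulness test occurs in 16 to 24% of all trials. That pair looks like the hypothesised pattern although half the reversal is present under mindfulness.

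**What an interval could exclude.** Define reversal as naloxone minus saline, positive when naloxone raises pain. With a true difference of zero, the chance that the upper limit of the 97.5% interval falls below a bound M is P(mean + 2.364 × estimated SE < M). For SD 0.30 to 0.424 this is 68 to 94% for 22 points, 35 to 65% for 15 points and 19 to 37% for 11 points.

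**The case against.** *The SAP has another route to evidence within mindfulness.* Its session factor includes baseline, so a paired simple effect could compare baseline with naloxone in that group. Relief that persists under what section 7 of the Protocol describes as full receptor blockade would be positive evidence against full opioid mediation, and would not rest on non-significance. This stands. A reader should not infer that the plan can produce no affirmative evidence about mindfulness. But the comparison does not exclude partial reversal, which needs the naloxone–saline difference.

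*The harm is hypothetical.* A reader might infer that the plan intends to treat p > .05 as proof of no opioid involvement. The documents do not support that: the objective is neutral and section 18 is conditional. The gap is the lack of any rule on how a negative result would be read.

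*The SD could be smaller.* This stands too. Within-patient correlation above 0.5 gives an SD of differences below 0.30 if 0.30 is per condition, and the Protocol expects covariates to reduce residual variance. At SD 0.232 the problem shrinks but remains.

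*The SAP's gate already limits error.* If reversal is equal in both groups (11 or 15 points, SD 0.30 to 0.424, .05), reversal in controls only is found in about 2% of trials when the two-level contrast is the gate. The figure of 19 to 25% requires reading the Protocol as ungated. In the 11-point case the overall drug effect is significant in 51 to 80% of trials. So a shared reversal is fairly well guarded against under the SAP. A smaller reversal under mindfulness is not.

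*Scale.* The percentages belong to the power calculation and do not convert directly to the supine-to-SLR change on a 0–10 rating.

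**Conclusion.** The concern holds. The hypothesis of no reversal under mindfulness is tested against saline only by a paired test of difference, which the SAP makes conditional on an unnamed interaction, and no margin or interval rule says what a negative result would mean. No planned test is wrong in itself, and a full 22-point reversal would usually be detected. The weakness is for partial reversal, where the table shows a substantial miss rate at every SD considered, and for the gate, which can leave the primary question without a mindfulness-specific answer if it is the two-level contrast. The sizes rest on the assumed SD of paired differences, on 30 completers per group and on the 11-point illustration; they are not predictions for the 0–10 endpoint. A reader might also infer that the sample size must rise or that an equivalence margin is required. Neither follows: an interval with an exclusion-style conclusion is enough. This should be settled before unblinding.

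**What to change.** In the Protocol (Data Analyses and Interpretation) and the SAP (Statistical Analysis Plan):

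1. Report the mindfulness-group naloxone–saline difference in the supine-to-SLR pain change with its confidence interval, whether or not any interaction is significant. Use the level that matches the multiplicity correction: 97.5% if .025 per outcome applies, as in the Protocol. The SAP gives no number and should state one. Word a negative conclusion as the size of reversal that the interval excludes, in the units of that endpoint, and not from non-significance.
2. Name the naloxone–saline group-by-drug contrast, with its interval, as the basis for any claim that the groups differ, and name it as the interaction that opens the SAP's other follow-up tests. Align the Protocol with the SAP on this gate.

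A margin fixed before unblinding is optional.

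The cost is wording and one interval per primary outcome, with no change to visits or sample size. The downside is that some results otherwise read as negative would be called inconclusive or limited. At SD 0.30 to 0.42 the trial can usually exclude a full reversal but often not a partial one, so a tight margin would often fail.
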